**ABSTRACT:**

**Introduction/Methods:** Pancreatic fibrosis is the end stage of chronic pancreatitis (CP), which leads to loss of acinar volume and secretory capacity, and ultimately pancreatic insufficiency (PI). CP and congenital PI affect the pediatric population, and are both increasingly recognized in children. PI has serious negative implications on a child's growth and health but, if diagnosed early, PI can be treated, minimizing the detrimental effects of PI. Currently, direct pancreatic function testing (PFT) via collection of pancreatic fluid is the "gold standard" for diagnosis of PI but it is an invasive testing that may require sedation or general anesthesia. Magnetic resonance cholangiopancreatography (MRCP) with secretin administration (MR-PFT) and MR elastography (MRE) may allow non-invasive, and potentially early diagnosis of CP and PI. Currently, however, normative data with which to compare MR-PFT and MRE results in pediatric patients with suspected CP/PI is not available. **Aims:** Herein, we propose to determine the normal range for secreted pancreatic fluid volume in response to secretin administration and determine the normal range for pancreatic parenchymal stiffness in a pediatric population that is not affected by pancreatic disease. Additionally, we will assess visibility of the pancreatic duct pre and post administration of secretin. To date, we have validated our MRCP technique and have successfully performed both MR-PFT and MRE in CP patients; however normative data is essential for validation of our non-invasive technique. **Conclusion:** Normative pediatric data derived from this study will provide a baseline against which future studies of pediatric patients with suspected CP and PI can be assessed. Additionally, the techniques described herein might also be leveraged in the future in the adult population.

**PURPOSE OF STUDY:**

**Collect normative data for pancreatic state (the size, volume, anatomy, biliary and vascular structures) as well as the volume of secreted fluid in response to secretin administration in a representative sample of healthy pediatric controls.**

**Determine secreted volumes:** *Hypothesis 1.* Total secreted fluid volume as measured by MR-PFT will correlate with subject size and age. *Exp 1.* MR-PFT will be performed in 50 healthy pediatric subjects including 25 subjects ages 6-11.9 years and 25 subjects 12-15.9 years. Secreted volumes will be correlated with subject age and height, weight, body mass index and body surface area.

**Collect normative data for pancreatic stiffness as measured by MR elastography.**

*Hypothesis 2.* Pancreatic parenchymal stiffness in the pediatric population will fall in a normative range similar to adult norms and will not depend on subject age or size. *Exp 2.* Pancreatic parenchymal stiffness will be measured in the same healthy cohort of 50 healthy pediatric subjects including 25 subjects ages 6-11.9 years and 25 subjects 12-15.9 years.

**Assess the relationship between pancreatic exocrine function, pancreatic stiffness and pancreatic parenchymal volume.** *Hypothesis 3.* Pancreatic exocrine function as measured by MR-PFT and pancreatic stiffness as measured by MRE will be dependent on pancreatic parenchymal volume. *Exp 3.* Secreted fluid volumes as measured by MR-PFT and pancreatic

stiffness as measured by MRE will be correlated with volumetric measurements of pancreatic parenchymal volume.

**Assess the effect of secretin on the visibility of the pancreatic duct.** *Hypothesis 4.* A subjective, blinded assessment of pancreatic duct visibility pre-and post-secretin will show an increase in visibility on post-secretin images.

We will also store this data to identify normative values in controls for pancreatic and any other gastrointestinal parameters in MRCP.

*Significance and Innovation:*

Our study will add significant information to the existing literature regarding diagnosis and staging of CP, and will set the foundation for using MR as a non-invasive biomarker for CP/PI in pediatrics. Our study is novel because it will investigate the use of MRI for assessing pancreatic anatomy, function, and stiffness in the pediatric population. It will also shed light on gastrointestinal anatomy and function in pediatric healthy controls which has not yet been described in the literature. Moreover, the results of our study will fill a knowledge gap regarding normal secretory function of the pancreas in children.

**BACKGROUND:**

Chronic pancreatitis (CP) is a morbid condition with poor quality of life, significant pain, and negative impact on growth, health and overall wellbeing. Late stages of the disease, manifest as parenchymal fibrosis and loss of function (pancreatic insufficiency (PI)), are easier to diagnose than mild and early stages (minimal change disease). If CP is recognized early, therapies to treat mild disease and halt the progression to PI could be applied. As such, studies geared toward early detection are needed to identify minimal change disease and allow early therapeutic intervention. Once PI is suspected, direct pancreatic function testing (PFT) is the gold standard for assessment of pancreatic exocrine function. PFTs, as currently performed, are invasive and require sedation/anesthesia. Potential non-invasive means of assessing pancreatic structure and function include magnetic resonance cholangiopancreatography (MRCP) and MR elastography (MRE). In adult patients, MRCP with secretin stimulation has been demonstrated to allow non-invasive assessment of pancreatic exocrine function. MRCP for assessment of pancreatic exocrine function (MR-PFT), however, has not been validated in children and normative data are not available, limiting the utility of this test in the pediatric population. MR Elastography uses transmitted vibrations to assess tissue stiffness and early studies have shown efficacy in measuring pancreatic stiffness in adult patients. By measuring pancreatic stiffness, MRE might be utilized as a non-invasive assessment measure of developing pancreatic fibrosis which may serve as a biomarker of minimal change CP.

In preparation for this study, we developed a protocol to measure pancreatic fluid volume secreted in response to secretin administration, confirmed feasibility of pancreatic stiffness measurements by MRE and analyzed our experience with MR in pediatric patients with pancreatic disease, primarily CP. We have a cohort of CP patients that have undergone MRCP with the proposed study protocol and we will continue to collect data on CP patients that undergo MR studies. The overall aim of this pilot-study is to collect MR-PFT and MRE data in a small group of normal pediatric subjects (with no history of pancreatic disease, CP/PI, or intestinal disease) to serve as a preliminary data set for a subsequent comparative study of MR-PFT and MRE in children with CP. The ultimate aim is to provide results that would position non-invasive MR studies as an accurate, sensitive, and specific alternative to standard modalities of CP diagnosis and therapy monitoring (endoscopic PFT (ePFT), endoscopic

retrograde cholangiopancreatography (ERCP), endoscopic ultrasound (EUS), and biopsy). **Our overall hypothesis is that normative ranges can be established for total secreted pancreatic fluid volume as measured by MR-PFT and for pancreatic stiffness as measured by MRE and that secreted volumes but *not* pancreatic stiffness will depend on subject age and size.**

### **STUDY DESIGN:**

This will be a single center prospective study of children with no history of pancreatic disease to quantify normal pancreatic volumes and secreted fluid volume (SV) in response to secretin administration as measured by MR-PFT. We will also assess the pancreatic stiffness by MR elastography as well as pancreatic duct visibility (pre-and post-secretin) in the same cohort.

#### *MR elastography:*

MRE equipment consists of an active and a passive driver system. The passive driver is connected to the active driver in the equipment room by a wave-guide with a hollow plastic tube. The active driver generates low amplitude 60 Hz vibrations which are passed via pneumatic pressure to the passive driver which is placed on the patient's abdomen. The initiation and cessation of the vibrations are controlled by the MR pulse sequence programmed and embedded as part of the scanner software. The MRE pulse sequence does not bypass any scanner safety standards as specified by the manufacturer. The MRE sequence will produce magnitude and phase images at multiple levels in the pancreas. After the MRE magnitude and phase images are obtained, the data is converted into quantitative images displaying the stiffness of the pancreatic parenchyma. Stiffness and quantitative mean stiffness values are generated from the phase images. The MRE sequence being used as part of this study is an investigational sequence with which we have experience in both the clinical and research environment. The investigational sequence will be performed in such a way that the Food and Drug Administration (FDA) general MR safety guidelines cannot be overridden and/or exceeded.

#### *Secretin:*

Synthetic human secretin is a peptide hormone with an amino acid sequence identical to naturally occurring secretin. The main action is to increase the secretion of pancreatic juice, including bicarbonate by stimulating the exocrine pancreas thereby assisting in the diagnosis of exocrine pancreatic dysfunction. Secretin is FDA approved for pancreatic stimulation use in adults. We regularly use secretin in clinical practice at CCHMC. A limited MRCP with secretin stimulation with a dose of 0.2 mcg/kg (maximum of 16 mcg) will be performed and post-processed as detailed below.

#### *MR imaging:*

All studies will be performed on a 1.5T GE HDx MRI scanner (General Electric; Milwaukee, WI) using the 8-channel Torso coil. The following sequences will be obtained through the upper abdomen:

#### Pre-Secretin:

Axial 3D T1 GRE (LAVA)  
Axial fat saturated T2 fast spin echo (FSE)  
Axial 3D GRE magnetic resonance elastography (MRE)  
Axial T2 map  
Coronal 3D fast relaxation fast spin echo (FrFSE)  
Coronal fat saturated T2 SSFSE

Post-Secretin:

Coronal fat saturated T2 SSFSE at 1, 5, 10 and 15 minutes after Secretin injection

Coronal 3D FrFSE

*MR post-processing:*

MR-PFT:

Total secreted fluid volume in response to secretin will be determined from the pre- and post-secretin coronal T2 SSFSE using commercially available software (ImageJ, MatLab) by selecting a signal intensity threshold which isolates intraluminal fluid in the duodenum and proximal jejunum. A region of interest will then be drawn on each image inclusive of thresholded pixels, to determine the area (mm^2) of fluid signal. The area of fluid signal on each image will then be multiplied by the image slice thickness and all slice values will be summed to determine a fluid volume over the entire imaged volume.

MRE:

MR elastography images will be post-processed using software leased from Resoundant (Rochester, MN) with pancreatic parenchymal stiffness expressed as a mean stiffness (kPa) for the pancreatic neck, body, and tail.

Parenchymal volume:

Pancreatic parenchymal volume will be measured by manual segmentation of the pancreas using commercially available software (MIM, MIM Software Inc.; Cleveland, OH).

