**Assess the effect of secretin on the visibility of the pancreatic duct.**

Frequencies and rankings will be compared with Fischer exact test and Wilcoxon rank sum tests to compare visualization of the pancreatic duct pre- and post-secretin.

*Power calculation:*

To establish relationship between secreted fluid volume and subject body size or age, we base a power calculation on analysis of MR-PFT data in 19 CP patients and the assumption that secreted volume is correlated with age in this sample of patients. In a linear regression analysis of these patients, the observed residual standard error is approximately 39, with an  $R^2 \sim 0.40$ . The observed regression coefficient is 5.274, and standard deviation of predictor age is  $\sim 5.816$ . If this holds in a general population, we require at least 15 normal subjects to have a significant regression coefficient at 0.05 level, and 80% power.

Additionally, from the previously reported study of normal adult patients by Mensel et al. [25], the coefficient of variation (CV) of secreted volume (TEV in the paper) at various time points from secretin injection ranged from 0.30 to 0.51. Given that we plan to enroll subjects in two age groups (6-11.9 and 12-15.9 years old), 25 subjects in each age group will provide 80% chance that the 95% confidence interval of mean secreted volume will be within 12% to 20% of the mean value, depending on the actual CV observed.

Therefore, we plan to enroll a total of 50 evaluable subjects in the study to meet both needs above.

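### Fluid volume is defined as area times slice thickness, which is exact only for contiguous slices, and the plan states neither thickness, gap nor contiguity

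*Combined protocol and SAP*

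**What the plan says.** Under MR post-processing, the MR-PFT paragraph says that total secreted volume "will be determined from the pre- and post-secretin coronal T2 SSFSE". After the fluid area has been outlined on each image, the volume is obtained as follows: "The area of fluid signal on each image will then be multiplied by the image slice thickness and all slice values will be summed". The stated aim is "to determine a fluid volume over the entire imaged volume".

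The post-secretin series is listed as "Coronal fat saturated T2 SSFSE at 1, 5, 10 and 15 minutes after Secretin injection"; a matching series is taken before secretin. The MR imaging section fixes the equipment: "All studies will be performed on a 1.5T GE HDx MRI scanner", with one type of coil. Neither place gives the slice thickness, the gap or the spacing of the SSFSE series, or says whether the slices are contiguous.

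The Statistical analysis section then summarizes these volumes by means, standard deviations and 95% confidence intervals, regresses them on age and body size and, if feasible, fits quantile regressions to describe a normal range.

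**The concern.** Summing area times thickness counts only the fluid inside the slices. If the slices are separated, fluid lying between them is not counted. If they overlap, some is counted twice. The multiplier that works in either case is the distance between slice centres, which equals the thickness only when the gap is zero. The formula as written has no gap term, and the documents do not supply the condition that would make one unnecessary.

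At stake is the absolute scale of the norm. The Abstract presents the normative data as a baseline for future studies of children with suspected disease. If the volumes carry a hidden factor that depends on local slice geometry, a site with different geometry cannot use them correctly. Such a factor would not widen the confidence intervals, and it would not shrink with more children.

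**Working it through.** **Inputs.** From the MR-PFT paragraph: volume = sum of areas × thickness. From the Power calculation: "The observed regression coefficient is 5.274"; "the observed residual standard error is approximately 39"; the "standard deviation of predictor age is" about 5.816; R² about 0.40; at least 15 subjects for 80% power at the 0.05 level. That section gives no unit for the slope or the residual error. Not given anywhere: thickness T and gap G. I write g = G/T and treat it as an assumption, from 0% to 50%.

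**Step 1: the plan's own figure.** Effect size f² = (5.274 × 5.816 / 39)² = 0.619, which implies R² = 0.619/1.619 = 0.38, consistent with the stated 0.40. A two-sided slope t-test at 0.05 with n − 2 degrees of freedom and noncentrality √n × 0.7865 has power 0.771 at n = 14 and 0.804 at n = 15. The stated 15 reproduces.

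**Step 2: effect of a gap on volume.**
- Plan: ΣA × T.
- Volume of the whole slab: ΣA × (T + G).
- Ratio: T/(T + G) = 1/(1 + g), so the understatement is g/(1 + g).

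| Assumed gap, % of thickness | Understatement |
|---|---|
| 0 | 0% |
| 5 | 4.8% |
| 10 | 9.1% |
| 20 | 16.7% |
| 25 | 20.0% |
| 50 | 33.3% |

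For example, an assumed 5 mm slice with a 0.5 mm gap gives 5/5.5 = 0.909. If the pre- and post-secretin series share the same gap, the factor carries straight through to their difference.

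**Step 3: effect of a constant gap on the planned analyses.** Means, standard deviations, range limits and slopes are all divided by 1 + g. Taking the plan's slope and residual error as the true values, for illustration:
- g = 10%: slope 5.274/1.1 = 4.79; residual error 39/1.1 = 35.5.
- g = 20%: slope 5.274/1.2 = 4.40; residual error 39/1.2 = 32.5.

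In both cases the factor cancels in f², which stays at 0.619. R², p-values, power and the required 15 therefore do not change. Nor does the coefficient of variation, so the plan's precision target of 12% to 20% of the mean is also unaffected.

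**The case against.** The strongest reply is that no gap is documented. The aim of covering the whole imaged volume fits contiguous slices, for which the formula is exact. This stands: a reader might infer that the volumes are wrong, and the documents do not support that. They leave open whether the formula is right.

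A second reply is that a constant gap does little harm. It leaves the test of Hypothesis 1 intact. It also cancels in relative comparisons with the centre's own chronic pancreatitis cohort, which the Background says was imaged with the same protocol, provided the geometry matched. Images are kept in the research archive, so volumes could be rescaled later. This stands too and lowers the severity, but it does not answer the point for the absolute norms.

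A reader might also infer that gaps are widened to cover larger children, so that the slope on age or size is distorted. Such a gap could matter. With an assumed mean of 100 at age 11 and the plan's slope over ages 6 to 16, a gap rising from 0% to 20% gives a slope of 3.16 (40% lower), while one falling from 20% to 0% gives 6.48 (23% higher). But no section says that geometry is adapted to body size. A single centre, one scanner model and an established protocol point towards standard acquisition without proving it. A larger child covered by more slices at the same spacing causes no such error. The direction is unknown, and the assumed mean has no source in the documents. These figures show sensitivity only.

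Finally, it is tempting to set a 17% to 20% understatement against the 12% to 20% precision target. That compares a scale error with sampling error, and the target, being relative to the mean, does not move.

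**Conclusion.** The measurement is under-specified; no error is demonstrated. As written, the volume rule is correct only for contiguous slices, and the documents neither state contiguity nor give the figures needed to check it. If there is a gap, the absolute normative volumes, their range and the slope are understated by g/(1 + g): 0% at no gap, 9% at 10% and 17% at 20%. The gap sizes are assumptions. For a constant gap, the correlation tests, the coefficient of variation and the sample size stand. A size-related distortion of the slope is not supported by the documents. The severity is minor, but the correction costs almost nothing and concerns the study's main measurement.

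**What to change.** In the MR-PFT paragraph, replace the slice-thickness multiplier with centre-to-centre slice spacing, defined as thickness plus any inter-slice gap and read from the image header for each series. Report the SSFSE thickness and gap alongside the normative values.

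The result is identical if slices are contiguous. If they are not, it puts the volumes on the correct scale, and because spacing is read series by series it also removes any bias from gaps that differ between children or time points.

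The cost is one phrase in the protocol and one line in the report. The acquisition does not change, and archived images can be handled the same way. I would not ask for extra slices in larger children: the documents do not show whether these would fit within the 15–20 second breath-hold, and the spacing rule does not need them.

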### **DURATION:**

This initial pilot study is anticipated to take approximately 12 months but we will continue up to 24 months if we are not able to meet the recruitment target the first year.

### **RECRUITMENT & CONSENT OF PARTICIPANTS:**

*Subject Recruitment:*

Recruited subjects will have no history of pancreatic disease and will be identified through review of patients presenting for non-abdominal imaging examinations. Patients presenting for musculoskeletal MRI examinations will likely be the major source for recruited patients. In the last 2 years, 1297 musculoskeletal MR examinations have been done in pediatric patients, ages 6 -15 years, at our institution, providing a ready source for recruitment. Subjects may additionally be recruited through public recruitment using existing clinical trial recruitment services at CCHMC, including advertising within our institution to raise awareness of the study. CCHMC employees may be invited to enroll their children in the study; they would be invited by the research coordinator. Subject charts will be reviewed for evidence of pancreatitis or other pancreatic disease prior to/during enrollment. Following initial screening, subjects will be contacted by the study coordinator or an investigator and enrolled after informed consent is obtained. During enrollment, absence of exclusion criteria will be confirmed with a questionnaire completed prior to imaging.

50 evaluable subjects will be recruited evenly divided as follows:

25 subjects age 6-11.9 years

25 subjects age 12-15.9 years

*Inclusion Criteria:*

1. Subjects between the ages of 6 and 15.9 years.
2. Subjects without a documented history of (or suggestive of) pancreatic disease.

*Exclusion Criteria:*

1. History of pancreatic disease, liver disease, intra-abdominal neoplasm, abdominal inflammatory process such as inflammatory bowel disease (IBD), or systemic illness that may affect pancreatic state (e.g. cystic fibrosis).
2. Subjects with surgical hardware/implanted devices making them ineligible for MRI (e.g. pacemaker or other implanted medical device not approved for MRI).
3. Subjects who require any form of sedation or general anesthesia for MRI.
4. Subjects unable to breath-hold for the required 15-20 second imaging sequence.
5. Subjects who are pregnant or less than 12 months post-partum.

*Process of obtaining Consent:*

In accordance with the International Conference on Harmonization – Good Clinical Practices (ICH-GCP) and local legislation, all participants/families will be fully informed about the study, and the parents will give written informed consent prior to enrollment in the study and prior to any study specific procedures being performed. Participants  $\geq 11$  years of age will be asked to sign an assent form prior to participating in the study.

All participants will be asked to complete a metal screening form prior to participation in the study, regardless of whether or not they have done so in the past. This will ensure the MR screening information is up-to-date for anyone who participates in this protocol.

Females who are able to get pregnant will be screened with a urine pregnancy test prior to imaging. Results will be shared with subject and parent, if applicable.

Subjects will be reminded that participation in research is completely voluntary. Coercion is eliminated by having the subjects sign an assent document and the parent/guardian signs the consent document. Time will be given for families to read the consent documents and for any questions to be answered.

